8.4.3 UNANTICIPATED PROBLEM REPORTING

Incidents or events that meet the OHRP criteria for UPs require the creation and completion of an UP report form. It is the site investigator's responsibility to report UPs to their IRB and to the DCC/study sponsor. The UP report will include the following information:

- Protocol identifying information: protocol title and number, PI's name, and the IRB project number;
- A detailed description of the event, incident, experience, or outcome;
- An explanation of the basis for determining that the event, incident, experience, or outcome represents an UP;

• A description of any changes to the protocol or other corrective actions that have been taken or are proposed in response to the UP.

To satisfy the requirement for prompt reporting, UPs will be reported using the following timeline:

- UPs that are SAEs will be reported to the IRB and to the DCC/study sponsor within <insert timeline in accordance with policy> of the investigator becoming aware of the event.
- Any other UP will be reported to the IRB and to the DCC/study sponsor within <insert timeline in accordance with policy> of the investigator becoming aware of the problem.
- All UPs should be reported to appropriate institutional officials (as required by an institution's written reporting procedures), the supporting agency head (or designee), and OHRP within

8.4.4 EVENTS OF SPECIAL INTEREST

Not applicable.

8.4.5 REPORTING OF PREGNANCY

Although pregnancy and lactation are not considered adverse events, it is the responsibility of investigators or their designees to report any pregnancy or lactation in a subject (spontaneously reported to them), including the pregnancy of a male subject's female partner that occurs during the trial or within 120 days of completing the trial or 30 days following cessation of treatment. All subjects and female partners of male subjects who become pregnant must be followed to the completion/termination of the pregnancy. Any subject who becomes pregnant during the study, must be promptly withdrawn from the study and discontinue further study treatment. Pregnancy outcomes of spontaneous abortion, missed abortion, benign hydatidiform mole, blighted ovum, fetal death, intrauterine death, congenital anomaly, ectopic pregnancy, miscarriage and stillbirth must be reported as serious events (Important Medical Events). If the pregnancy continues to term, the outcome (health of infant) must also be reported. Such events must be reported within 24 hours of their knowledge of the event to Celgene using the Serious Adverse Event Form. Because the effect of the Celgene medicinal product on sperm is unknown, pregnancies in partners of male subjects exposed to a Celgene medicinal product will be reported by the Investigator within 24 hours of their knowledge of the event using the Serious Adverse Event Form. Depending on local legislation, this may require prior consent of the partner. Follow-up information regarding the outcome of the pregnancy and any postnatal sequelae in the infant will be required.

9 CLINICAL MONITORING

Data will be captured in OnCore, Moffitt's electronic Clinical Trials Database. For each subject enrolled, the electronic CRF must be completed by the assigned data manager or other authorized study staff. Any paper forms should be typed or filled out indelible ink and must be legible. Errors should be crossed out but not obliterated, the correction inserted, and the change initialed and dated by the investigator or his/her authorized delegate. This also applies to records for those subjects who fail to complete the study. If a subject stops dosing or terminates from the study, the dates and reasons must be noted on the CRF. If a subject terminates from the study because of toxicity, thorough efforts should be made to clearly document the outcome. Regulatory documents and case report forms will be monitored internally according to Moffitt Cancer Center monitoring policies. The monitoring will include source data verification, utilizing research subjects' medical records. The investigator should ensure the accuracy, completeness, legibility, and timeliness of the data reported to the protocol monitoring committee.

10 STATISTICAL CONSIDERATIONS

10.1 STATISTICAL AND ANALYTICAL PLANS

This is a phase II study with interim analysis for futility using Simon's two-stage design^{46,47} for the anti-PD1 therapy naïve and refractory subjects as follows:

Cohort 1: Anti-PD1 therapy naïve subjects:

Patients will be treated with CC-122 plus Nivolumab. The primary end point is response rate. The null hypothesis that the true response rate is 40% will be tested against a one-sided alternative of 60%. Targeting 90% power and 10% type I error, 28 evaluable subjects will be enrolled in stage 1 (n=28); if \leq 11 responders by RECIST – further enrollment will be stopped to this arm for futility. Otherwise enrollment will continue for an additional 13 patients in stage 2 for a total cohort sample size of 41 evaluable subjects. The null hypothesis will be rejected if 21 or more responses are observed in 41 patients.

Cohort 2: Anti-PD1 refractory subjects:

This cohort includes subjects who have demonstrated progression on previous anti-PD1 therapy and for whom continuation/resumption of an anti-PD1 agent would not be likely to elicit a radiographic response. Retrospective data using ipilimumab suggest a response of 10% following prior anti-PD1 therapy. For this cohort, we have set the null hypothesis rate to 10% with an alternative hypothesis of 30%. This sample size will be 25 if full accrual (16 patients in stage 1; If 2 or more responses - proceed to full accrual). The null hypothesis will be rejected is 5 or more subjects experience an objective response to therapy. This design yields a type I error rate of 9.5% with a power of 90%.

The maximum number of patients to be enrolled assuming complete enrollment will be 66 (41 + 25); minimum would be 44.

10.2 ANALYSIS OF THE SECONDARY ENDPOINT(S)

- All toxicity analyses will be collated according to grade and frequency. This will include all events
 considered possibly, probably, or definitely related to study therapy.
- Progression free survival will be calculated from the start of study therapy till the first documentation of disease progression, death, or change of treatment. Subjects receiving ongoing therapy at the time of data analysis will be censored.
- 3. Overall survival will be calculated from the start of therapy till death from any cause. Subjects alive at

the time of data analysis will be censored.

10 3 FFFICACY ANALYSIS

Objective response rate is the primary end point in this combination trial involving an immune checkpoint inhibitor in combination with an immunomodulatory agent. Response rates per RECIST 1.1 will be evaluated.

RECIST as assessed by the investigator will be used as the primary response rate efficacy end-point and make treatment decisions.

Immunotherapeutic agents such as nivolumab and pembrolizumab may produce antitumor effects by potentiating endogenous cancer-specific immune responses, which may be functionally anergic. The response patterns seen with such an approach may extend beyond the typical time course of responses seen with cytotoxic agents, and can manifest a clinical response after an initial increase in tumor burden or even the appearance of new lesions. Standard RECIST criteria may not provide a complete response assessment of immunotherapeutic agents such as nivolumab, therefore the irRECIST have been developed to encompass this. This will also be assessed as a secondary end-point of efficacy.

Broadly, irRECIST includes the concept of treatment beyond progression, if radiologic imaging shows PD, tumor assessment should be repeated ≥ 4 weeks later in order to confirm PD with the option of continuing treatment, while awaiting radiologic confirmation of progression. If repeat imaging shows a reduction in the tumor burden compared to the initial scan demonstrating PD, treatment may be continued as per treatment calendar. If repeat imaging confirms progressive disease, subjects will be discontinued from trial therapy. In determining whether or not the tumor burden has increased or decreased, Investigators should consider all target lesions as well as non-target lesions.

In subjects who have initial evidence of radiological PD, it is at the discretion of the treating physician whether to continue a subject on study treatment, until repeat imaging is obtained a minimum of 4 weeks later. This decision should be based on the clinical judgment of the subject's overall clinical condition, including performance status, clinical symptoms, and laboratory data. Subjects may receive treatment while waiting for confirmation of PD if they are clinically stable as defined by the following criteria:

- Absence of signs and symptoms indicating disease progression
- No decline in ECOG performance status
- Absence of rapid progression of disease
- Absence of progressive tumor at critical anatomical sites (e.g., cord compression) requiring urgent alternative medical intervention

When feasible, subjects should not be discontinued until progression is confirmed. This allowance to continue treatment despite initial radiologic progression takes into account the observation that some subjects can have a transient tumor flare in the first few months after the start of immunotherapy, but with subsequent disease response. Subjects that are deemed clinically unstable are not required to have repeat imaging for confirmation of progressive disease.

Subjects who continue treatment beyond initial radiographic progression while awaiting confirmation imaging will need to be re-consented for their ongoing treatment with nivolumab and avadomide on the clinical trial. All other elements of the main consent including description of reasonable foreseeable risks or discomfort, and other alternative therapy will still apply.

Stopping Rules for Excessive Toxicity:

To evaluate the safety, we will monitor the toxicity continuously using a Pocock-type boundary.⁴⁹ Sequential boundaries will be used to monitor dose-limiting toxicity (DLT) rate. As this is a phase II trial, DLT is defined as discontinuation of one or both drugs secondary to toxicity. The accrual will be halted if excessive numbers of DLTs are seen, that is, if the number of DLTs is equal to or exceeds b_n out of n patients with full follow-up (per table below). This is a Pocock-type stopping boundary that yields the probability of crossing the boundary at most 25% when the rate of DLT is equal to the acceptable DLT rate of 25%.

Table: Stopping rules for toxicity

The trial will be stopped for review if the number of dose limiting toxicities (DLTs) is equal to or exceeds b_n out of n patients with completed follow-up. This is targeting 25% DLT with 25% probability of early stopping for each cohort. For cohort 1, the maximum accrued number of patients will be 41 while the maximum accrued number of patients will be 25.

For cohort 1, the maximum accrued number of patients will be 41. The trial will be stopped if the number of dose limiting toxicities is equal to or exceeds b_n out of n patients with completed follow-up.

Number of Patients, n	1	2	3	4	5	6	7	8	9	10	11	12	13	14	15	16	17	18	19	20
Boundary, b _n	-	2	3	3	4	4	4	5	5	5	6	6	6	7	7	7	8	8	8	9
Number of Patients, n	21	22	23	24	25	26	27	28	29	30	31	32	33	34	35	36	37	38	39	40
Boundary, b _n	9	9	10	10	10	11	11	11	11	12	12	12	13	13	13	14	14	14	15	15
Number of Patients, n	41	42	43	44	45	46	47	48	49	50	51	52	53	54	55	56	57	58	59	60
Boundary, bn	15																			

This boundary is equivalent to testing the null hypothesis, after each patient, that the event rate is equal to 0.25, using a one-sided level 0.09 test.

For cohort 2, the maximum accrued number of patients will be 25. The trial will be stopped if the number of dose limiting toxicities is equal to or exceeds b_n out of n patients with completed follow-up.

```
Number of Patients, n 1 2 3 4 5 6 7 8 9 10 11 12 13 14 15 16 17 18 19 20 Boundary, bn - 2 3 3 3 4 4 5 5 5 5 6 6 6 6 7 7 7 8 8 8 8

Number of Patients, n 21 22 23 24 25 26 27 28 29 30 31 32 33 34 35 36 37 38 39 40 Boundary, bn 9 9 9 10 10
```

This boundary is equivalent to testing the null hypothesis, after each patient, that the event rate is equal to 0.25, using a one-sided level 0.11 test.

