Secondary: (1) To assess the toxicity of this combination. (2) To determine the progression-free survival and overall survival with this combination. (3) Examine blood and tissue-based biomarkers that will further our understanding of the complex interplay between the metabolic needs/changes in the tumor and the immune microenvironment.

Population:

Adults with advanced melanoma who are appropriate for treatment with anti-PD1 therapy or who are appropriate to resume anti-PD1 therapy after prior progression on anti-PD1 therapy with the goal of reversing resistance.

Number of Sites

This study will be conducted at the Moffitt Cancer Center

Study Agent(s) and Administration:

Oral CC-122 at 2mg daily for 5 consecutive days every 7 days, with intravenous nivolumab (240mg) in days 1 and 15 within a 28-day cycle.

[figure not shown]
Study Duration:

Subjects will receive up to 52 weeks of therapy. Decision to continue beyond this will be made based on response at that time. Based on planned futility analyses and enrollment across cohorts, the total number of subjects is anticipated to be 44-66.

Participant Duration:

Participants to be followed for up to 24 months following completion of study therapy.

SCHEMATIC OF STUDY DESIGN

KEY ROLES

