- This should occur after the participant has completed all planned therapy or been discontinued from protocol therapy due to progression or toxicity. This visit should occur within 30 days of the last administered study drug or at the time of start of new anti-neoplastic therapy for melanoma, whichever is sooner. If study therapy related toxicity has not resolved by the date of this evaluation, follow up should continue till resolution of toxicity. Note that this is not necessary for toxicities that require long-term replacement therapy (e.g., thyroid replacement therapy, steroid replacement therapy, management of immune-mediated hyperglycemia).
- Record adverse events as reported by participant or observed by investigator.
- Record vital signs and physical examination
- Collect blood for EOT. Obtain biopsy of metastatic site if feasible, especially in case of progression to help inform mechanisms of resistance to anti-PD1 therapy.
- Record participant's adherence to treatment regimen.
- Subjects who discontinue trial treatment for a reason other than disease progression will
 move into the Follow-Up Phase and should be assessed every 12 weeks (± 7 days) by
 radiologic imaging to monitor disease status up to 24 months after the final patients is
 enrolled or until receiving treatment outside of this protocol. Every effort should be made to
 collect information regarding disease status until the start of new anti-neoplastic therapy,
 disease progression, death, or end of the study. Information regarding post-study antineoplastic treatment will be collected if new treatment is initiated.

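### The toxicity boundary as worded leaves out DLTs already seen in patients still in follow-up, so it halts later than it needs to; and no DLT period is given for the 25% rate

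*Combined protocol and SAP*

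**What the plan says.** Under Stopping Rules for Excessive Toxicity, Section 10.3 says "we will monitor the toxicity continuously using a Pocock-type boundary". It adds that "DLT is defined as discontinuation of one or both drugs secondary to toxicity". Accrual halts "if the number of DLTs is equal to or exceeds b_n out of n patients with full follow-up". The text introducing each cohort's table uses a second wording: "The trial will be stopped if the number of dose limiting toxicities is equal to or exceeds b_n out of n patients with completed follow-up". The stated operating property is a crossing probability of "at most 25% when the rate of DLT is equal to the acceptable DLT rate of 25" percent, repeated as "This is targeting 25% DLT with 25% probability of early stopping for each cohort". The tables run to 41 patients (cohort 1) and 25 (cohort 2).

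Section 10.3 gives no length for full or completed follow-up and no period for the 25% rate. Other sections state periods for other purposes:
- Therapy lasts up to 52 weeks, with optional continuation (6.1.2).
- "Participants to be followed for up to 24 months following completion of study therapy" (Protocol Summary).
- Imaging follow-up applies to patients who stop for reasons other than progression (7.1).
- Adverse events are recorded until 7 days, and SAEs until 30 days, after the last day of participation (8.3).

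None of these is tied to the boundary. Section 8.4.2 says that a data and safety plan will define DLTs and the criteria for stopping. That plan is not among the documents, and Section 10.3 does not refer to it.

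**The concern.** A DLT is known on the day a drug is stopped for toxicity. A patient without a DLT is known to be free of one only when the period ends. The wording treats both alike and makes each wait for the end of follow-up. Suppose five of the first ten treated patients have had a DLT, which meets the boundary at n = 10 (b = 5). Nothing that happens later can undo this, yet the rule as written waits until the tenth patient has completed follow-up. With a 12-month period and 2 patients per month (both assumed), up to 12 × 2 = 24 more patients could enrol during that wait.

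Separately, a 25% rate with no period attached is not a defined rate. The same patients can be well below 25% over one month and well above it over a year. This is the only numeric toxicity boundary in the documents, so both its timing and its sensitivity matter.

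**Working it through.** **1. The plan's own figure.** Inputs from Section 10.3: the printed cohort 1 values b_n for n = 1 to 41, and an acceptable rate of 0.25. Add one patient at a time with status known, carry the binomial distribution of the DLT count along paths still below b_n, and sum the probability that leaves at each n.

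| True DLT rate | P(cross), cohort 1 |
|---|---|
| 0.25 | 0.248 |
| 0.30 | 0.452 |
| 0.40 | 0.849 |
| 0.50 | 0.986 |

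The 25% limit is reproduced. The cohort 2 row is broken in the text available, so it was rebuilt from the stated 0.11 level: 0.244 at a rate of 0.25. The boundary itself is not in error.

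**2. Counting DLTs as they occur.** Order patients by first dose. Let D_n(t) be the DLTs seen by calendar time t among the first n treated, S_n their final number over a DLT period W, and t_n the first-dose date of patient n.
- Full follow-up counting crosses at n if S_n ≥ b_n, and acts at t_n + W.
- The alternative acts at the first t at which D_n(t) ≥ b_n for any n.

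D_n(t) never falls, and it equals S_n by t_n + W. So the alternative crosses exactly when S_n ≥ b_n for some n, and no later than t_n + W. The crossing probabilities in step 1 are unchanged.

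**3. What this gains.** Assumptions not in the documents: Poisson accrual of 1, 2 or 3 per month, a 3-month pause after patient 28 (Section 10.4 halts enrolment for the futility analysis but gives no duration), a 12-month DLT period, and onset from early (12 × Beta(1,4) months) to uniform. At least 6,000 cohorts were simulated per scenario. The table shows mean enrolled of 41 at the halt, among cohorts that cross, at 1 / 2 / 3 per month.

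| Scenario | Full follow-up | Count as they occur (early to uniform onset) |
|---|---|---|
| 50% rate | 21 / 29 / 35 | 12–17 / 15–23 / 18–28 |
| 40% rate | 24 / 32 / 36 | 16–20 / 19–26 / 22–31 |
| 50% rate, no pause | 21 / 32 / 39 | 12–17 / 16–24 / 19–31 |

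In simulation the two rules crossed in the same cohorts every time, and the alternative was never later.

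**4. Why the period still has to be stated.** Hold one assumed process fixed: 50% DLT by 12 months. Let f be the period as a fraction of 12 months. The rate within the period is 0.5 × f for uniform onset and 0.5 × [1 − (1 − f)^4] for early onset. Put each rate through the recursion in step 1.

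| DLT period | Rate, uniform / early | P(cross), uniform / early |
|---|---|---|
| 28 days (f = 28/365) | 0.038 / 0.137 | 0.002 / 0.033 |
| 3 months | 0.125 / 0.342 | 0.026 / 0.64 |
| 6 months | 0.250 / 0.469 | 0.25 / 0.97 |
| 12 months | 0.500 / 0.500 | 0.986 / 0.986 |

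A short period also sits badly with the DLT definition. A 28-day period could not include a CC-122 discontinuation triggered by more than 4 weeks of interruption (6.1.3.1), or a nivolumab discontinuation triggered by more than 6 weeks of delay (6.1.3.2, with its exception).

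**5. Why the counting rule needs exact wording.** Two informal repairs lose the 25% (assumed 2 per month, uniform onset, periods of 4, 12, 26 and 52 weeks):
- If patients enter n when their status becomes known, DLTs enter early and non-DLTs late. Crossing at a 25% rate becomes 0.30, 0.45, 0.65 and 0.88.
- If total DLTs are compared only with b at the number dosed so far, it becomes 0.20, 0.15, 0.09 and 0.07.

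Checking every first-n group, as in step 2, avoids both.

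**The case against.** The strongest reply is that the missing period may be in the data and safety plan named in Section 8.4.2, and that the same section provides continuous review by the investigator, the research group and the monitoring committee. That stands: absence from Section 10.3 does not show absence from the trial, and the boundary is not the only protection. It does not answer the counting point, because the full or completed follow-up condition is part of the boundary as written.

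A second objection is that first-dose counting inherits the undefined period. That also stands. A reader might infer that the counting change alone closes the gap. It cannot, because it crosses in exactly the cohorts that full follow-up over the same period would.

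A third is that late-onset DLTs with fast accrual still halt late (about 28 of 41 at 3 per month with uniform onset). That is true, but it is still earlier than the 35 under the present wording.

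Two stronger readings are not supported. One could set the DLT rate to 50% in every candidate period and conclude that a short period simply halts sooner. But 50% in one month and 50% in a year are different toxicity profiles; for a single profile, step 4 shows that a short period mostly fails to fire. One could also read full follow-up as 52 weeks of therapy plus 24 months, so that the rule acts after most or all of accrual. The 24-month periods concern participant follow-up and disease imaging, whereas a DLT is the stopping of a study drug and cannot newly occur once therapy has ended.

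**Conclusion.** The point holds in two parts. First, the wording delays the halt without any gain in error control. Under the step 3 assumptions, at 2 patients per month and a 50% rate, 15–23 rather than about 29 of 41 patients would be enrolled when cohort 1 halts. That no halt is later, and that crossing stays at 0.248 for a 25% rate, follows from the construction and needs no assumption about accrual or onset, only a common DLT period. The sizes do rest on assumed accrual, pause, period and onset.

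Second, the period attached to the 25% is not stated, and it governs whether the rule fires: 0.002–0.033 against 0.986 for one assumed process. The printed cohort 1 table is not wrong, and nothing here shows that the trial lacks safety oversight. This should be clarified before the boundary is applied.

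**What to change.** 1. In Section 10.3, replace the full/completed follow-up condition with a counting rule: order patients in each cohort by first dose, count each DLT when it occurs, and halt as soon as, for any n, the first n treated patients include at least b_n DLTs. Apply the printed tables to the first 41 treated in cohort 1 and the first 25 in cohort 2.
2. State the DLT period to which the 25% refers, as set by the sponsor, and reconcile it and the DLT definition with the data and safety plan in Section 8.4.2. No length is proposed here.

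The cost is a few sentences and tracking DLTs by order of first dose; no new patients or data are needed. One limit should be acknowledged. Section 5.4.1 allows replacement of patients who miss the cycle 1 dosing threshold, so more than 41 or 25 may be treated, and those beyond these numbers fall outside the tables. If the sponsor prefers to cover them, the tables must be extended and the crossing probability restated. For cohort 1, extending at the stated 0.09 level gives 0.252 at n = 42 and 0.267 at n = 50, slightly above the stated 25% limit.
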